5.3 Polymyalgia-like syndrome	
Definition: Characterized by marked pain and stiffness in proximal upper and/or lower extremities and no signs of true muscle inflammation such as CK elevation or EMG findings of myositis. No true muscle weakness, difficulty in active motion related to pain	
Diagnostic work-up	
G1 Complete rheumatologic history regarding differential diagnosis and examination of all joints and skin Check for symptoms of temporal arteritis, such as headache or visual disturbances; refer to ophthalmologist if present, and consider temporal artery biopsy ANA, RF, anti-CCP CK to evaluate differential diagnosis of myositis Inflammatory markers (ESR, CRP) Monitoring: ESR, CRP	
G2: Complete history and examination as above; autoimmune tests as required for differential diagnosis; early referral to a rheumatologist	
G3-4: As for G2; see rheumatologist advice and review	
Grading	Management
G1: Mild stiffness and pain	Continue ICPI Initiate analgesia with acetaminophen and/or NSAIDs if there are no contraindications
G2: Moderate stiffness and pain, limiting age-appropriate instrumental ADL	Consider holding ICPI and resuming upon symptom control, prednisolone < 10 mg; if worsens, treat as per G3 Initiate prednisone 20 mg/d or equivalent; if symptoms improve, start to taper dose after 3-4 weeks If no improvement or need for higher dosages after 4 weeks, escalate to G3 Consider referral to rheumatology
G3-4: Severe stiffness and pain, limiting self-care ADL	Hold ICPI and may resume, in consultation with rheumatology, if recover to G1 or less; however, note that cases of toxicity returning upon rechallenge have been reported. Referral to rheumatology Should initiate prednisone 20 mg/d or equivalent. If no improvement or need for higher dosages for prolonged time, may offer a corticosteroid-sparing agent such as methotrexate or IL-6 inhibition with tocilizumab (Note: As caution, IL-6 inhibition can cause intestinal perforation; while this is extremely rare, it should not be used in patients with colitis or GI metastases). Consider admission for pain control
All recommendations are expert consensus based, with benefits outweighing harms, and strength of recommendations are moderate.	
Abbreviations: ADL, activities of daily living; ANA, antinuclear antibodies; CCP, citrullinated protein antibody; CK, creatine kinase; CRP, C-reactive protein; DMARD, disease-modifying antirheumatic drug; EMG, electromyography; ESR, erythrocyte sedimentation rate; ICPI, immune checkpoint inhibitor; IL, interleukin; irAE, immune-related adverse event; IV, intravenous; IVIG, intravenous immunoglobulin; LDH, lactate dehydrogenase; NSAID, nonsteroidal anti-inflammatory drug; PCP, Pneumocystis pneumonia ; RF, rheumatoid factor; TNF, tumor necrosis factor.	

Table 6. Management of Renal irAEs in Patients Treated With ICPIs	
6.0 Renal Toxicities	

Nephritis and renal dysfunction: diagnosis and monitoring
 
For any suspected immune-mediated adverse reactions, exclude other causes
 
Monitor patients for elevated serum creatinine prior to every dose
 
Routine urinalysis is not necessary, other than to rule out UTIs, etc; nephrology may consider further
 
If no potential alternative cause of AKI identified, then one should forego biopsy and proceed directly with immunosuppressive therapy
 
Swift treatment of autoimmune component important
	
6.1 Nephritis	
Definition: Inflammation of the kidney affecting the structure	
Grading	Management
G1: Creatinine level increase of > 0.3 mg/dL; creatinine 1.5-2.0 × over baseline	Consider temporarily holding ICPI, pending consideration of potential alternative etiologies (recent IV contrast, medications, fluid status) and baseline renal function. A change that is still < 1.5 ULN could be meaningful
G2: Creatinine 2-3 × above baseline	Hold ICPI temporarily Consult nephrology Evaluate for other causes (recent IV contrast, medications, fluid status, etc); if other etiologies ruled out, administer 0.5-1 mg/kg/d prednisone equivalents If worsening or no improvement: 1 to 2 mg/kg/d prednisone equivalents and permanently discontinue treatment If improved to G1 or less, taper corticosteroids over 4-6 weeks If no recurrence of chronic renal insufficiency, discuss resumption of ICPI with patient after taking into account the risks and benefits.
G3: Creatinine > 3 × baseline or > 4.0 mg/dL; hospitalization indicated	Permanently discontinue ICPI
G4: Life-threatening consequences; dialysis indicated	Consult nephrology Evaluate for other causes (recent IV contrast, medications, fluid status, etc) Administer corticosteroids (initial dose of 1-2 mg/kg/d prednisone or equivalent)

Additional considerations
 
Monitor creatinine weekly
 
Reflex kidney biopsy should be discouraged until corticosteroid treatment has been attempted
	
6.2 Symptomatic nephritis: follow-up	
Grading	Management
G1	If improved to baseline, resume routine creatinine monitoring
G2	If improved to G1, taper corticosteroids over at least 3 weeks before resuming treatment with routine creatinine monitoring If elevations persist > 7 days or worsen and no other cause found, treat as G3
G3	If improved to G1, taper corticosteroids over at least 4 weeks If elevations persist > 3-5 days or worsen, consider additional immunosuppression (eg, mycophenolate)
G4	If improved to G1, taper corticosteroids over at least 4 weeks If elevations persist > 2-3 days or worsen, consider additional immunosuppression (eg, mycophenolate)
All recommendations are expert consensus based, with benefits outweighing harms, and strength of recommendations are moderate.	
Abbreviations: AKI, acute kidney injury; G, grade; ICPI, immune checkpoint inhibitor; irAE, immune-related adverse event; IV, intravenous; ULN, upper limit of normal; UTI, urinary tract infection.	

Table 7. Management of Nervous System irAEs in Patients Treated With ICPIs	
7.0 Nervous System Toxicities	
7.1 Myasthenia gravis	

Definition: Fatigable or fluctuating muscle weakness, generally more proximal than distal. Frequently has ocular and/or bulbar involvement (ptosis, extraocular movement abnormalities resulting in double vision, dysphagia, dysarthria, facial muscle weakness). May have neck and/or respiratory muscle weakness. (Note: May occur with myositis and/or myocarditis. Respiratory symptoms may require evaluation to rule out pneumonitis, myocarditis. Miller Fisher variant of Guillain-Barré syndrome (ophthalmoparesis) and the oculobulbar myositis (ptosis, ophthalmoparesis, dysphagia, neck and respiratory weakness) with ICPI may have overlapping symptoms.
	

Diagnostic work-up
 
 AChR and antistriated muscle antibodies in blood; if AChR antibodies are negative, consider muscle specific kinase and lipoprotein-related 4 antibodies in blood Pulmonary function assessment with NIF and VC CPK, aldolase, ESR, CRP for possible concurrent myositis Consider MRI of brain and/or spine, depending on symptoms to rule out CNS involvement by disease or alternate diagnosis If respiratory insufficiency or elevated CPK, troponin T, perform cardiac examination with ECG and TTE for possible concomitant myocarditis Neurologic consultation Electrodiagnostic studies, including neuromuscular junction testing with repetitive stimulation and/or jitter studies, NCS to exclude neuropathy, and needle EMG to evaluate for myositis 	
Grading	Management
All grades	All grades warrant work-up and intervention given potential for progressive myasthenia gravis to lead to respiratory compromise
No G1	
G2: Some symptoms interfering with ADL MGFA severity class 1 (ocular symptoms and findings only) and MGFA severity class 2 (mild generalized weakness)	
Hold ICPI and may resume in G2 patients (MGFA 1 and 2) only if symptoms resolve⁸⁷
 
Should consult neurology
 
Pyridostigmine starting at 30 mg orally three times a day and gradually increase to maximum of 120 mg orally four times a day as tolerated and based on symptoms
 
Administer corticosteroids (prednisone, 1-1.5 mg/kg orally daily) if symptoms G2; wean based on symptom improvement

G3-4: Limiting self-care and aids warranted, weakness limiting walking, ANY dysphagia, facial weakness, respiratory muscle weakness, or rapidly progressive symptoms, or MGFA severity class 3-4 moderate to severe generalized weakness to myasthenic crisis	
Permanently discontinue ICPI
 
Admit patient, may need ICU-level monitoring
 
Neurology consult
 
Continue corticosteroids and initiate IVIG 2 g/kg IV over 5 days (0.4 g/kg/d) or plasmapheresis for 5 days
 
Frequent pulmonary function assessment
 
Daily neurologic review

Additional considerations
 
 Avoid medications that can worsen myasthenia: β-blockers, IV magnesium, fluoroquinolones, aminoglycosides, and macrolides Initially a 5-day course of plasmapheresis or a 2 g/kg course of IVIG over 5 days 1-2 mg/kg methylprednisolone daily, wean based on symptom improvement Pyridostigmine, wean based on improvement ICPI-associated myasthenia gravis may be monophasic, and additional corticosteroid-sparing agents may not be required 	
7.2 Guillain-Barré syndrome	

Definition: Progressive, most often symmetrical muscle weakness with absent or reduced deep tendon reflexes. Often starts with sensory symptoms/neuropathic pain localized to lower back and thighs. May involve extremities (typically ascending weakness but not always), facial, respiratory, and bulbar and oculomotor nerves. May have dysregulation of autonomic nerves.
	

Diagnostic work-up
 
 Neurologic consultation MRI of spine with or without contrast (rule out compressive lesion and evaluate for nerve root enhancement/thickening) Lumbar puncture: CSF typically has elevated protein and often elevated WBCs; even though this is not typically seen in classic Guillain-Barré syndrome, cytology should be sent with any CSF sample from a patient with cancer. Serum antiganglioside antibody tests for Guillain-Barré syndrome and its subtypes (eg, anti-GQ1b for Miller Fisher variant associated with ataxia and ophthalmoplegia) Electrodiagnostic studies to evaluate polyneuropathy Pulmonary function testing (NIF/VC) Frequent neurochecks 	
Grading	Management
All grades	
Warrant work-up and intervention given potential for progressive Guillain-Barré syndrome to lead to respiratory compromise
 
Note: There is no G1 toxicity

G1: Mild, none	NA
G2: Moderate, some interference with ADL, symptoms concerning to patient	
Discontinue ICPI
 
Admission to inpatient unit with capability of rapid transfer to ICU-level monitoring
 
Start IVIG (0.4 g/kg/d for 5 days for a total dose of 2 g/kg) or plasmapheresis.
 
Corticosteroids are usually not recommended for idiopathic Guillain-Barré syndrome; however, in ICPI-related forms, a trial is reasonable (methylprednisolone 2-4 mg/kg/d), followed by slow corticosteroid taper
 
Pulse corticosteroid dosing (methylprednisolone 1 g/d for 5 days) may also be considered for G3-4 along with IVIG or plasmapheresis
 
Frequent neurochecks and pulmonary function monitoring
 
Monitor for concurrent autonomic dysfunction
 
Nonopioid management of neuropathic pain
 
Treatment of constipation/ileus

G3-4: Severe, limiting self-care and aids warranted, weakness limiting walking, ANY dysphagia, facial weakness, respiratory muscle weakness, or rapidly progressive symptoms	
(continued on following page)	

Table 7. Management of Nervous System irAEs in Patients Treated With ICPis

7.0 Nervous System Toxicities

7.1 Myasthenia gravis

Definition: Fatigable or fluctuating muscle weakness, generally more proximal than distal. Frequently has ocular and/or bulbar involvement (ptosis, extraocular movement abnormalities resulting in double vision, dysphagia, dysarthria, facial muscle weakness). May have neck and/or respiratory muscle weakness. (Note: May occur with myositis and/or myocarditis. Respiratory symptoms may require evaluation to rule out pneumonitis, myocarditis. Miller Fisher variant of Guillain-Barré syndrome (ophthalmoparesis) and the oculobulbar myositis (ptosis, ophthalmoparesis, dysphagia, neck and respiratory weakness) with ICPi may have overlapping symptoms.

Diagnostic work-up

- AChR and antistriated muscle antibodies in blood; if AChR antibodies are negative, consider muscle specific kinase and lipoprotein-related 4 antibodies in blood
- Pulmonary function assessment with NIF and VC
- CPK, aldolase, ESR, CRP for possible concurrent myositis
- Consider MRI of brain and/or spine, depending on symptoms to rule out CNS involvement by disease or alternate diagnosis
- If respiratory insufficiency or elevated CPK, troponin T, perform cardiac examination with ECG and TTE for possible concomitant myocarditis
- Neurologic consultation
- Electrodiagnostic studies, including neuromuscular junction testing with repetitive stimulation and/or jitter studies, NCS to exclude neuropathy, and needle EMG to evaluate for myositis

Grading	Management
All grades	All grades warrant work-up and intervention given potential for progressive myasthenia gravis to lead to respiratory compromise
No G1	
G2: Some symptoms interfering with ADL MGFA severity class 1 (ocular symptoms and findings only) and MGFA severity class 2 (mild generalized weakness)	Hold ICPi and may resume in G2 patients (MGFA 1 and 2) only if symptoms resolve ⁸⁷ Should consult neurology Pyridostigmine starting at 30 mg orally three times a day and gradually increase to maximum of 120 mg orally four times a day as tolerated and based on symptoms Administer corticosteroids (prednisone, 1-1.5 mg/kg orally daily) if symptoms G2; wean based on symptom improvement
G3-4: Limiting self-care and aids warranted, weakness limiting walking, ANY dysphagia, facial weakness, respiratory muscle weakness, or rapidly progressive symptoms, or MGFA severity class 3-4 moderate to severe generalized weakness to myasthenic crisis	Permanently discontinue ICPi Admit patient, may need ICU-level monitoring Neurology consult Continue corticosteroids and initiate IVIG 2 g/kg IV over 5 days (0.4 g/kg/d) or plasmapheresis for 5 days Frequent pulmonary function assessment Daily neurologic review
Additional considerations	
Avoid medications that can worsen myasthenia: β -blockers, IV magnesium, fluoroquinolones, aminoglycosides, and macrolides	
Initially a 5-day course of plasmapheresis or a 2 g/kg course of IVIG over 5 days	
1-2 mg/kg methylprednisolone daily, wean based on symptom improvement	
Pyridostigmine, wean based on improvement	
ICPi-associated myasthenia gravis may be monophasic, and additional corticosteroid-sparing agents may not be required	

7.2 Guillain-Barré syndrome

Definition: Progressive, most often symmetrical muscle weakness with absent or reduced deep tendon reflexes. Often starts with sensory symptoms/neuropathic pain localized to lower back and thighs. May involve extremities (typically ascending weakness but not always), facial, respiratory, and bulbar and oculomotor nerves. May have dysregulation of autonomic nerves.

Diagnostic work-up

- Neurologic consultation
- MRI of spine with or without contrast (rule out compressive lesion and evaluate for nerve root enhancement/thickening)
- Lumbar puncture: CSF typically has elevated protein and often elevated WBCs; even though this is not typically seen in classic Guillain-Barré syndrome, cytology should be sent with any CSF sample from a patient with cancer.
- Serum antiganglioside antibody tests for Guillain-Barré syndrome and its subtypes (eg, anti-GQ1b for Miller Fisher variant associated with ataxia and ophthalmoplegia)
- Electrodiagnostic studies to evaluate polyneuropathy
- Pulmonary function testing (NIF/VC)
- Frequent neurochecks

Grading	Management
All grades	Warrant work-up and intervention given potential for progressive Guillain-Barré syndrome to lead to respiratory compromise Note: There is no G1 toxicity
G1: Mild, none	NA
G2: Moderate, some interference with ADL, symptoms concerning to patient	Discontinue ICPi Admission to inpatient unit with capability of rapid transfer to ICU-level monitoring Start IVIG (0.4 g/kg/d for 5 days for a total dose of 2 g/kg) or plasmapheresis. Corticosteroids are usually not recommended for idiopathic Guillain-Barré syndrome; however, in ICPi-related forms, a trial is reasonable (methylprednisolone 2-4 mg/kg/d), followed by slow corticosteroid taper Pulse corticosteroid dosing (methylprednisolone 1 g/d for 5 days) may also be considered for G3-4 along with IVIG or plasmapheresis Frequent neurochecks and pulmonary function monitoring Monitor for concurrent autonomic dysfunction Nonopioid management of neuropathic pain Treatment of constipation/ileus
G3-4: Severe, limiting self-care and aids warranted, weakness limiting walking, ANY dysphagia, facial weakness, respiratory muscle weakness, or rapidly progressive symptoms	

(continued on following page)

Table 7. Management of Nervous System irAEs in Patients Treated With ICPis (continued)	
7.0 Nervous System Toxicities	
Grading	Management

G1: Mild, no interference with function and symptoms not concerning to patient. Note: Any cranial nerve problem should be managed as moderate.
 
G2: Moderate, some interference with ADL, symptoms concerning to patient (ie, pain but no weakness or gait limitation)
 
G3-4: Severe, limiting self-care and aids warranted
	
Hold ICPi and discuss resumption with patient only after taking into account the risks and benefits
 
Consider empirical antiviral (IV acyclovir) and antibacterial therapy until CSF results
 
Once bacterial and viral infection are negative, may closely monitor off corticosteroids or consider oral prednisone 0.5-1 mg/kg or IV methylprednisolone 1 mg/kg if moderate/severe symptoms

7.6 Encephalitis	

Definition: As for aseptic meningitis, need to exclude infectious causes, especially viral (ie, HSV). Confusion, altered behavior, headaches, seizures, short-term memory loss, depressed level of consciousness, focal weakness, speech abnormality
	

Diagnostic work-up
 
Neurologic consultation
 
MRI of brain with or without contrast may reveal T2/fluid-attenuated inversion recovery changes typical of what is seen in autoimmune encephalopathies or limbic encephalitis or may be normal
 
Lumbar puncture: check cell count and protein glucose and perform Gram stain, culture, PCR for HSV and other viral PCRs depending on suspicion, cytology, oligoclonal bands, autoimmune encephalopathy, and paraneoplastic panels.
 
May see elevated WBC count with lymphocytic predominance and/or elevated protein
 
EEG to evaluate for subclinical seizures
 
Blood: metabolic, CBC, ESR, CRP, ANCA (if suspect vasculitic process), thyroid panel including TPO and thyroglobulin
 
Rule out concurrent anemia/thrombocytopenia, which can present with severe headaches and confusion
	
Grading	Management

G1: Mild, no interference with function and symptoms not concerning to patient. Note: Any cranial nerve problem should be managed as moderate.
 
G2: Moderate, some interference with ADL, symptoms concerning to patient (ie, pain but no weakness or gait limitation)
 
G3-4: Severe, limiting self-care and aids warranted
	
Hold ICPi and discuss resumption with patient only after taking into account the risks and benefits
 
As above for aseptic meningitis, suggest concurrent IV acyclovir until PCR results obtained and negative
 
Trial of methylprednisolone 1-2 mg/kg
 
If severe or progressing symptoms or oligoclonal bands present, consider pulse corticosteroids methylprednisolone 1 g IV daily for 3-5 days plus IVIG 2 g/kg over 5 days
 
If positive for autoimmune encephalopathy antibody and limited or no improvement, consider rituximab or plasmapheresis in consultation with neurology

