5.7 Study Drug Discontinuation Criteria

Subjects **must** be permanently discontinued from BOTH study drugs (INCMGA00012 and INCAGN01876) if any one or more of the following occurs:

- Grade 2 or higher toxicity [per NCI CTCAE v 5.0] that is at least possibly related to one of the study drugs AND does not improve with optimal medical management to grade 1 or less within 12 weeks from last dose of study drugs or results in subject being unable to taper off corticosteroids (or, if on corticosteroids prior to the toxicity, unable to taper down to subject's baseline/pre-toxicity dose) within 12 weeks from last dose of study drugs, with the following exceptions:
 - Grade 2 Nervous System toxicity (e.g., leg weakness, aphasia, etc) that is *due to* intratumoral/peritumoral enlargement (contrast-enhancing or T2/FLAIR) or intratumoral/peritumoral cerebral edema
 - Grade 3-4 Nervous System toxicity (e.g., leg weakness, aphasia, etc) that is *due to* intratumoral/peritumoral enlargement (contrast-enhancing or T2/FLAIR) or intratumoral/peritumoral cerebral edema AND improves to grade 2 or less within 7 days of optimal medical management
 - Grade 3 Cerebral Edema
 - Grade 4 Cerebral edema that improves to grade 3 within 7 days of optimal medical management

- Any grade endocrinopathy that is controlled by hormone replacement
- Grade 4 irAE, as defined in [Section 9.1.2, *Immune-Related Adverse Events*](#), with the following exception:
 - Grade 4 endocrinopathy that is controlled by hormone replacement
- Grade 3 hepatitis, pneumonitis, nephritis, myocarditis, pericarditis, encephalitis, myasthenia gravis, posterior- or pan-uveitis, episcleritis, peripheral neuropathy (including Guillain-Barre syndrome), autoimmune hemolytic anemia, acquired hemophilia, or autonomic neuropathy
- Recurrent Grade 2 pneumonitis
- Any grade transverse myelitis
- The subject becomes pregnant.
- Consent is withdrawn by the subject.
 - Note:** Consent withdrawn means that the subject can no longer be followed and no additional data can be collected. Subjects may choose to discontinue study treatment and remain in the study to be followed for progression and survival.
- Further participation would be injurious to the subject's health or well-being, in the investigator's medical judgment.
- Confirmed radiographic progression of disease per modified RANO criteria (as defined in [Section 7](#)).

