and described in detail in **Appendix 1** with specific application to this protocol. These recommendations include management of the toxicity itself, as well as guidance for dose interruptions/delays of the investigational agents. There are no dose reductions or dose escalations permitted for either investigational agent.

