APPENDIX 1. Management guidelines for Immune-Related Adverse Events (irAEs)*

*ICPi = immune checkpoint inhibitor; in this protocol, this refers to BOTH study drugs INCMGA00012 and INCAGN01876.

*These tables are copied directly from the original publication for convenience (Brahmer et al, J Clin Oncol 2018).

Table 1. Management of Skin irAEs in Patients Treated With ICPIs	

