G2: Asymptomatic (AST or ALT > 3.0 to \leq 5 \times ULN and/or total bilirubin > 1.5 to \leq 3 \times ULN)	
Hold ICPI temporarily and resume if recover to G1 or less on prednisone \leq 10 mg/d
 
For grade 2 hepatic toxicity with symptoms, may administer corticosteroid 0.5-1 mg/kg/d prednisone or equivalent if the abnormal elevation persists with significant clinical symptoms in 3-5 days
 
Increase frequency of monitoring to every 3 days
 
Infliximab might not be the most appropriate treatment option in the situation of immune-mediated hepatitis given the potential risk of idiosyncratic liver failure (Note: No clear evidence shows the liver toxicity from infliximab from other studies)
 
In follow-up, may resume ICPI treatment followed by taper only when symptoms improve to G1 or less and corticosteroid \leq 10 mg/d; taper over at least 1 month
 
Patients should be advised to stop unnecessary medications and any known hepatotoxic drugs

G3: Symptomatic liver dysfunction, fibrosis by biopsy, compensated cirrhosis, reactivation of chronic hepatitis (AST or ALT 5-20 \times ULN and/or total bilirubin 3-10 \times ULN)	
Permanently discontinue ICPI
 
Immediately start corticosteroid 1-2 mg/kg methylprednisolone or equivalent
 
If corticosteroid refractory or no improvement after 3 days, consider mycophenolate mofetil or azathioprine (if using azathioprine should test for thiopurine methyltransferase deficiency)
 
Laboratories at daily or every other day; consider inpatient monitoring for patients with AST/ALT > 8 \times ULN and/or elevated TB 3 \times ULN
 
Increase frequency of monitoring to every 1-2 days
 
Infliximab might not be the most appropriate treatment option in the situation of immune-mediated hepatitis given the potential risk of liver failure (Note: No clear evidence shows that the liver toxicity from infliximab from other studies); alternatives include non-TNF-α agents as systemic immunosuppressants
 
If no improvement is achieved with corticosteroids or for patients on combination therapy with a novel agent, with standard chemotherapy, or with targeted therapy, refer to hepatologist for further pathologic evaluation of hepatitis
 
Corticosteroid taper can be attempted around 4-6 weeks; re-escalate if needed; optimal duration unclear

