G2: Moderate pain associated with signs of inflammation, erythema, or joint swelling, limiting instrumental ADL	Hold ICPI and resume upon symptom control and on prednisone ≤ 10 mg/d Escalate analgesia and consider higher doses of NSAIDs as needed If inadequately controlled, initiate prednisone or prednisolone 10-20 mg/d or equivalent for 4-6 weeks If improvement, slow taper according to response during the next 4-6 weeks; if no improvement after initial 4-6 weeks, treat as G3 If unable to lower corticosteroid dose to < 10 mg/d after 3 months, consider DMARD Consider intra-articular corticosteroid injections for large joints Referral to rheumatology
G3-4: Severe pain associated with signs of inflammation, erythema, or joint swelling; irreversible joint damage; disabling; limiting self-care ADL	Hold ICPI temporarily and may resume in consultation with rheumatology, if recover to G1 or less Initiate oral prednisone 0.5-1 mg/kg If failure of improvement after 4 weeks or worsening in meantime, consider synthetic or biologic DMARD Synthetic: methotrexate, leflunomide Biologic: consider anticytokine therapy such as TNF-α or IL-6 receptor inhibitors. (Note: As caution, IL-6 inhibition can cause intestinal perforation; while this is extremely rare, it should not be used in patients with colitis.) Test for viral hepatitis B, C, and latent/active TB test prior to DMARD treatment Referral to rheumatology.
Additional considerations	
Early recognition is critical to avoid erosive joint damage. Corticosteroids can be used as part of initial therapy in inflammatory arthritis, but due to likely prolonged treatment requirements, physicians should consider starting corticosteroid-sparing agents earlier than one would with other irAEs Oligoarthritis can be treated early on with intra-articular corticosteroids; consider early referral. Consider PCP prophylaxis for patients treated with high dose of corticosteroids for > 12 weeks, as per local guidelines.	

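### Appendix 1 item 7.6 allows resumption to be discussed after Grade 3-4 encephalitis, Section 5.7 requires both drugs to stop for good, and no text says which governs

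*Combined protocol and SAP*

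**What the plan says.** Section 5.7 lists the events after which a subject *must* stop both drugs for good. One bullet begins "Grade 3 hepatitis, pneumonitis, nephritis, myocarditis, pericarditis, encephalitis, myasthenia gravis" and carries no exception. Another covers any Grade 4 irAE as defined in Section 9.1.2, and its only exception is "Grade 4 endocrinopathy that is controlled by hormone replacement". Encephalitis is therefore a stopping event at Grade 3 by name, and at Grade 4 through the irAE bullet.

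Appendix 1, item 7.6 (Encephalitis), lists Grades 1, 2 and 3-4. Its only drug instruction is "Hold ICPi and discuss resumption with patient only after taking into account the risks and benefits". No line under that item mentions permanent discontinuation at any grade.

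The header note to Appendix 1 says of the term ICPi that "in this protocol, this refers to BOTH study drugs INCMGA00012 and INCAGN01876". The same note says "These tables are copied directly from the original publication for convenience". Section 5.8.1 refers the reader to the appendix for management of specific irAEs, described there "with specific application to this protocol". It calls the content recommendations, which include guidance on interrupting or delaying the investigational agents.

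**The concern.** The two places give different drug actions for the same event, at the same grade, for the same two drugs. Section 1.3.1.3 lists encephalitis as a potentially serious irAE of INCMGA00012. Section 5.8.1 anticipates that adding the GITR agonist could make immune toxicity more frequent or more severe than with PD-1 inhibition alone. Cohort A and sub-arm 1 of Cohort B also receive brain radiosurgery.

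Item 7.6 is where a clinician would look for the work-up of confusion, seizures or focal weakness, and the hold instruction stands beside that work-up. What is at stake is rechallenge with both drugs after a severe neurological event for which the protocol's stopping rule does not allow it.

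**Working it through.** No arithmetic applies to the conflict itself. The check is a comparison of texts.

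1. **Same drugs.** Section 5.7 names both drugs. Appendix 1 defines ICPi as both drugs.

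2. **Same event and grade.** Section 5.7 names encephalitis at Grade 3 and reaches Grade 4 through the irAE bullet. Item 7.6 has a G3-4 line. The exceptions in Section 5.7 for nervous system toxicity due to tumor enlargement or edema belong to a different bullet, the one on unresolved toxicity, and do not soften the encephalitis bullet.

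3. **Different action.** Section 5.7 requires a permanent stop. Item 7.6 requires a hold, with resumption open to discussion.

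4. **Not an effect of text extraction.** Table 7 of the appendix is damaged in the text available, but item 7.6 contains no discontinuation wording however its rows are laid out. Item 7.7 (Transverse myelitis) has the same grade block and does call for permanent discontinuation, which matches Section 5.7.

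5. **The appendix does state permanent stops elsewhere.** For Grade 3 hepatitis (item 2.2) it reads "Permanently discontinue ICPI", in agreement with Section 5.7. A reader may therefore take the absence of such wording in item 7.6 as deliberate.

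6. **Which text governs.** Three things favor Section 5.7. Its wording is mandatory. Section 3.3 ends treatment once a Section 5.7 criterion is met, and Section 3.1.3 sends subjects who stop for a Section 5.7 reason to follow-up. Section 5.8.1 calls the appendix content recommendations. The statement that the appendix applies specifically to this protocol points the other way. No sentence ranks the two.

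7. **Other rows.** Item 5.1 (Inflammatory arthritis), G3-4, reads "Hold ICPI temporarily and may resume in consultation with rheumatology, if recover to G1 or less". Item 8.4 (Aplastic anemia), G3-4, has treatment stopped only until the event returns to Grade 1. These conflict with Section 5.7 only if the event is a CTCAE Grade 4 irAE, because neither condition is in the Grade 3 list.

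8. **Run-in.** Section 3.1 counts subjects who experience a Section 5.7 criterion. A Grade 3 encephalitis in the run-in therefore counts whatever is later done with the drugs.

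9. **Frequency.** Table 3 shows no encephalitis among the 37 + 132 + 15 + 15 = 199 participants given INCMGA00012 alone. The documents give no rate for the three-part regimen used here.

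**The case against.** The strongest reply is that the documents already show which rule controls. Section 5.7 is mandatory and Section 3.3 ends treatment on its criteria, while the appendix is a copied set of recommendations on holds and delays. The two can also both be obeyed: item 7.6 does not order resumption, so a site that holds and then stops permanently breaches neither. Harm would need a Grade 3-4 case, recovery, a clinician who overlooks a bullet naming encephalitis, and agreement in a single-center trial where Section 5.8.1 sends irAEs of Grade 2 or higher to the principal investigator at once.

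Most of this stands, and it limits the weight of the point. It does not remove it. That Section 5.7 prevails is an inference. The appendix cannot be read as covering holds only, since it contains permanent stops of its own. Discussion with the principal investigator lowers the risk without saying which rule applies.

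A reader might infer three stronger things that the documents do not support:

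- **That encephalitis is the only Grade 3 event in Section 5.7 on which the appendix disagrees.** This cannot be established. In the available text of Table 7 the myasthenia gravis and Guillain-Barré entries appear twice, the numbering then goes from 7.2 to 7.6, and one block has lost its heading. A count of agreeing entries, or a statement that some condition has no entry, would be unsafe.
- **That a probability of harm can be given.** Any such figure would rest on an assumed rate. It would also be the chance of a case of encephalitis, not of re-exposure after one.
- **That the safety run-in could be miscounted.** Section 3.1 rules this out if it is followed.

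**Conclusion.** The inconsistency is real and concerns a safety instruction: the appendix permits consideration of rechallenge after an event for which the stopping rule forbids it, and no precedence is stated. Its size is modest. Only subjects with Grade 3-4 encephalitis, or with a CTCAE Grade 4 irAE in one of the lenient rows, could be affected. Their expected number in a trial planned for 32 subjects is small, although the rate for this combination is unknown. No endpoint, sample size, analysis or run-in count changes.

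The conclusion rests on the extracted text of item 7.6 being complete for the encephalitis entry. For the Grade 4 cases it also rests on the event being judged an irAE under Section 9.1.2. It should be corrected because a wrong rechallenge could seriously harm a patient and the correction costs almost nothing.

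**What to change.** Add one sentence to Section 5.8.1 and repeat it in the Appendix 1 header note: *Where Appendix 1 is more lenient than Section 5.7, Section 5.7 governs permanent discontinuation of the study drugs.* This settles item 7.6 and the Grade 4 rows together, without editing the copied tables.

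Optionally, annotate the G3-4 line of item 7.6: *permanently discontinue both study drugs per Section 5.7.* This puts the rule where the clinician will be reading. If the sponsor wants a further exception to the Grade 4 stop, it belongs in Section 5.7.

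The cost is one sentence in two places and, if wanted, one annotation. Nothing in the design or analysis changes.
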